8.4. Patient population studied

The trial population aims to include 858 babies who require the narrowest PICC (Premicath 1

French gauge (Fr)).

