8.4.3. Removal of patients from therapy or assessment

All babies will have their PICC removed at some point. Case report form (CRF) "Form 6:

Removal" records the reason for PICC removal. These include:

PICC no longer needed

Removed because of confirmed infection

Removed because of suspected infection

Damaged

Unintended removal

PICC blocked

Thrombosis

Clinically evident thrombophlebitis

Pre-specified duration of use reached

Malposition identified during x-ray

Babies will be observed for clinical follow-up for 48 hours after the PICC removal and a

retrospective review of key events will take place when the baby is discharged

home/dies/reached 26 weeks post randomisation, unless the parent/legal representative

instructs otherwise.

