8.7. Method of assignment to treatment

Full details of the randomisation procedure can be found in sections 6.3 and 9.2 of the protocol.

The randomisation list will be generated by a statistician (who is not involved with the PREVAIL

trial) at the CTU. Babies will be randomised to AM-PICC or S-PICC in a ratio of 1:1.

Randomisation will be stratified by centre. Babies will be randomised using a secure (24-hour)

web based randomisation programme controlled centrally by the CTU to ensure allocation

concealment. Details of block sizes can be found in the Statistics Trial File under section 4.

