9.2. Secondary outcomes

Outcomes captured up until 48 hours after PICC removal:

1. Rifampicin resistance in any isolate from blood/CSF culture.

2. Rifampicin resistance in any isolate from PICC tips.

3. Type of organism isolated from BSI.

4. Rate of BSI per 1000 PICC-days (including recurrent BSI).

5. Occurrence of 1 or more BSI.

6. Rate of catheter-related BSI per 1000 PICC days.

7. Rate of blood/CSF culture sampling per 1000 PICC days.

8. Duration of antimicrobial exposure from randomisation up to 48 hours after PICC

removal.

9. Time to PICC removal.

Outcomes captured up until discharge home from neonatal care/death/6 months post

randomisation:

10. Chronic lung disease 36 weeks postmenstrual age.

11. Necrotizing enterocolitis (NEC): Bell's stage II or III.

12. Treatment for retinopathy of prematurity.

13. Abnormalities on cranial ultrasound.

14. Time to full milk feeds after randomisation.

15. Total duration of parenteral nutrition from randomisation until discharge from NNU.

16. Death:

a) within 6 months (26 weeks) of randomisation

b) before discharge home from neonatal care

c) time to death

10. Determination of Sample Size

The sample size calculation can be found in section 9.4 of the protocol.

11. Study Framework

The overall objective for each of the study outcomes (primary and secondary) is to test the

superiority of AM-PICCs compared with S-PICCs.

12. Confidence Intervals, p-values and Multiplicity

All applicable statistical tests will be two-sided and will be performed using a 5% significance

level; confidence intervals presented will be 95%. No adjustment will be made for multiplicity

for the secondary outcomes. Percentages will be presented as 1 decimal place. Test statistics,

p-values, confidence intervals and measures of spread will be presented as 2 decimal places.

13. Timing and Objectives of Interim and Final Analyses

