17.4. Analysis of outcomes

17.4.1. Primary Outcome

The primary efficacy outcome is time to BSI based on any positive blood/CSF culture

(including fungal isolates) taken between 24 hours after randomisation until 48 hours after

PICC removal.

17.4.1.1. **Derivation**

The date and time that a sample was taken is recorded on CRF "Form 5: Microbiology". The

samples included for the primary outcome are those taken between 24 hours after

randomisation until 48 hours after PICC removal. The date and time of randomisation can be

found on CRF "Form 2: Randomisation". The date and time of PICC removal can be found on

CRF "Form 6: Removal". The unit of measurement will be hours.

BSI is defined as any positive culture recorded on CRF "Form 5: Microbiology" for the field

"organism cultured" (any culture except an entry of 'none') from blood or CSF samples. Any

'other' recorded organism will be referred to the clinical team for confirmation of whether this

is a positive culture. Organisms grown from 'other' sample types will also be referred to the

clinical team for confirmation of whether this constitutes the primary outcome.

All decisions made by the clinical team, will be made blinded to treatment allocation.

If there is a positive culture prior to the primary outcome time window and a positive culture in

the primary outcome time window:

• If the second positive culture is from the same isolate as the first and:

o there were less than 14 days between the two samples they should be

classified as the same episode of BSI and the positive culture within the primary

outcome time window will not be counted.

o there were 14 days of more between the two samples they should be classified

as two independent episodes of BSI and the positive culture within the primary

outcome time window will be counted.

If the second positive culture is from a different isolate to the first and:

o there were less than 24 hours between the two samples they should be

classified as the same episode of BSI and the positive culture within the primary

outcome time window will not be counted.

o there were 24 hours or more between the two samples they should be classified

as two independent episodes of BSI and the positive culture within the primary

outcome time window will be counted.

If there are multiple positive cultures within the primary outcome time window, each positive

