culture will be assessed using the criteria above and the first one that meets the definition will

be counted.

Survival times will be measured from the date and time of randomisation to the date and time

of the first sample, that meets the definition of independent episode of BSI outlined above.

For those not experiencing the primary outcome, they will be censored at death (date and time

found on Form 7a: Clinical Outcomes under section 1 question 3), 48 hours after PICC

removal or for those with no PICC inserted, 48 hours after randomisation. All censoring will be

assumed to be non-informative.

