17.4.1.2. Analysis

The following will be reported overall and split by sample type and treatment:

• Number of babies with sample taken in primary outcome time window (24 hours after

randomisation and up to 48 hours after PICC removal)

Number of samples taken in primary outcome time window

Number of babies with BSI in the POTW

This is a time to event outcome and will be analysed using the log-rank test and Kaplan-Meier

curves presented with the numbers at risk for each treatment group. The median and

interquartile range for time to BSI will be presented.

Cox proportional hazard regression models will be used if appropriate. However, since the

hazard of infection may not be constant post CVC insertion, non-proportional hazards survival

models will also be investigated. Results will be presented using Hazard Ratios and 95%

confidence intervals, along with the log-rank p-value.

Differences between date and time of randomisation and date and time of insertion will be

summarised using medians and IQR.

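### The primary BSI outcome is described by Kaplan-Meier and a median/IQR, which overstate the proportion of babies infected by a given day; cumulative incidence should be added

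*SAP*

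**What the plan says.** SAP section 17.4.1.1 limits the event to a window: the "samples included for the primary outcome are those taken between 24 hours after" randomisation and 48 hours after the PICC comes out. Time runs from randomisation. A baby without an event is censored at death, or at 48 hours after "removal or for those with no PICC inserted, 48 hours after randomisation. All censoring will be" assumed non-informative.

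Section 17.4.1.2 specifies a log-rank test, Kaplan-Meier curves with numbers at risk, hazard ratios with 95% confidence intervals and, as the descriptive summary, a median and "interquartile range for time to BSI will be presented". It does not say whether these quantiles come from the Kaplan-Meier curve or from infected babies only.

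Section 8.4.3 states that every baby's line will eventually be removed. Its list of removal reasons includes confirmed infection and "Removed because of suspected infection".

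The four sensitivity analyses in section 19.1 change the BSI definition or the time origin. None changes how removal or death is handled.

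**The concern.** Removal and death here are not ordinary loss to follow-up. By the definition of the outcome, a baby whose post-removal window has closed, or who has died, can no longer have the event. Kaplan-Meier treats these babies as still able to have it at the same rate as babies whose lines remain in. One minus Kaplan-Meier therefore describes a setting in which lines stay in, and not the share of babies in the trial who have a BSI by a given day. As every line comes out, nearly every event-free baby is affected.

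The median and IQR share the problem. If they are Kaplan-Meier quantiles, they may lie beyond the time when almost any line is in place. If they are taken among infected babies, they condition on having the outcome and do not describe the randomised groups.

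At stake is the absolute risk by day that a reader takes from the primary figure. No planned analysis estimates it.

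**Working it through.** **Inputs from the SAP.** The plan states: "The trial population aims to include 858 babies who require the narrowest PICC". It also states: "Babies will be randomised to AM-PICC or S-PICC in a ratio of 1:1". So 858/2 = 429 per arm. The figure of 858 cannot be reproduced from the SAP, which says: "The sample size calculation can be found in section 9.4 of the protocol". It serves here only to express numbers at risk.

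**Inputs that are assumed.** The SAP gives no BSI rate, line duration or death rate. I take a constant BSI hazard h of 12 or 20 per 1000 days, starting at 24 hours. Line time is exponential with mean m of 5 or 12 days from randomisation, and risk ends 2 days after removal. Deaths and babies with no line are ignored.

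**Formulas**, with t in days, t ≥ 2, and k = h + 1/m:
- One minus Kaplan-Meier: 1 − exp(−h(t − 1)).
- Cumulative incidence: 1 − exp(−h) + h·exp(−h)·[1 − exp(−k(t − 2))]/k.
- Fraction still at risk: exp(−h(t − 1))·exp(−(t − 2)/m).

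**One case in full** (h = 0.012, m = 5, day 28). One minus Kaplan-Meier is 1 − exp(−0.324) = 27.67%. With k = 0.212, cumulative incidence is 0.01193 + 0.011857 × (1 − exp(−5.512))/0.212 = 0.01193 + 0.05570 = 6.76%. The ratio is 4.09.

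**All four corners** (one minus Kaplan-Meier against cumulative incidence, in %; ratios taken before rounding):

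| h per 1000 days | m (days) | Day 7 | Day 14 | Day 28 | Ever infected |
|---|---|---|---|---|---|
| 12 | 5 | 6.95 vs 4.85 (1.43) | 14.44 vs 6.35 (2.28) | 27.67 vs 6.76 (4.09) | 6.79 |
| 12 | 12 | 6.95 vs 5.91 (1.18) | 14.44 vs 9.67 (1.49) | 27.67 vs 12.59 (2.20) | 13.63 |
| 20 | 5 | 11.31 vs 7.92 (1.43) | 22.89 vs 10.26 (2.23) | 41.73 vs 10.86 (3.84) | 10.89 |
| 20 | 12 | 11.31 vs 9.64 (1.17) | 22.89 vs 15.46 (1.48) | 41.73 vs 19.66 (2.12) | 20.95 |

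**Other shapes.** A second set of assumptions fixed the crude risk at 5%, 10% or 20% and the mean line time at 5, 8 or 12 days, with exponential, Weibull (shape 1.5) or lognormal (sigma 0.7) line times. The ratios were 1.04 to 1.44 at day 7, 1.31 to 2.29 at day 14 and 1.96 to 4.20 at day 28. Less dispersed line times thus shrink the early gap.

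**The median.** The Kaplan-Meier median falls at t = 1 + ln 2/h, which is day 58.8 at 12 per 1000 and day 35.7 at 20 per 1000. The expected number at risk there is 429 × 0.5 × exp(−(t − 2)/m). For m = 5 to 12 this gives 0.003 to 1.9 babies per arm at 12 per 1000, and 0.3 to 13 at 20 per 1000.

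In simulation under the second set (400 trials of 429 babies per arm per scenario), the median was reached in 2–14% of arms at 5% crude risk, 7–30% at 10% and 45–94% at 20%. The upper quartile was reached in 1–38%. The lower quartile fares better: 11–37% at 5% crude risk, 50–91% at 10% and 100% at 20%.

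**The case against.** The strongest reply is that the planned inference is untouched. The log-rank test and Cox model compare cause-specific hazards, and censoring at removal and death is legitimate for that. A reader might infer from the Kaplan-Meier problem that the primary test or hazard ratio is invalid. The SAP does not support that, and this part of the reply stands.

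Absolute risk is also not absent. Section 17.4.1.2 reports the number of babies with BSI in the window, section 17.5.5 compares the proportion with at least one BSI, and section 17.5.4 gives a rate per 1000 PICC-days. A difference between the Kaplan-Meier figure and the 17.5.5 percentage is no contradiction, because they are different quantities. This stands too, but none of these gives risk by day.

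The largest overstatements lie late in the curve, where few babies remain, and the planned numbers at risk will show it. A reader might infer a several-fold error throughout; under the assumptions above it is well below twofold at day 7.

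It is also tempting to read the removal reasons as proof that censoring is informative. A line removed for confirmed infection will usually already have a counted positive culture, and after removal for suspected infection a positive sample still counts for 48 hours. That sicker babies keep lines longer is not stated in the SAP. The removal reasons make a blanket assumption doubtful, but they do not show bias in the hazard ratio.

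Finally, withdrawn and lost babies contribute up to that point (section 18), and this censoring still needs the non-informative assumption. Deleting the statement outright would be wrong.

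**Conclusion.** The point holds as one about describing absolute risk. Under the plan's definition, one minus Kaplan-Meier overstates the proportion of babies with BSI by a given day, and no planned analysis estimates that proportion correctly over time. The direction follows from the event definition alone. The size rests on assumed inputs: about 1.2 to 1.4-fold at day 7, 1.5 to 2.3-fold at day 14 and 2.1 to 4.1-fold at day 28 with exponential line times, and somewhat less at the lower end with other shapes.

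The median and IQR are undefined as written, and neither reading serves. A Kaplan-Meier median is mostly unreachable at 5–10% crude risk. At 20% it is often reached but rests on few babies. A median among infected babies conditions on the outcome.

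The documents do not support a claim that the primary comparison is wrong. This is an inexpensive improvement to how the primary outcome is reported.

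**What to change.** In section 17.4.1.2, add the Aalen-Johansen cumulative incidence of BSI by arm, with death and the end of the post-removal window as competing events. Report it with 95% confidence intervals at fixed days, for example 7, 14 and 28, in place of the median and IQR. Keep the log-rank test, the Cox model and the Kaplan-Meier curve with numbers at risk, and label them as cause-specific.

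In section 17.4.1.1, restrict the non-informative assumption to withdrawal and loss to follow-up.

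The cost is one figure and one table with standard software; the primary test does not change. There are two drawbacks. Readers have one more quantity to understand. Cumulative incidence also reflects any effect of the catheter on line duration, so it should be read beside time to PICC removal (section 17.5.9).

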17.4.2. Secondary Outcomes

For outcomes which require samples to be taken, events are only considered on samples

taken between 24 hours after randomisation until 48 hours after PICC removal. This time

period is referred to as the "primary outcome time window".

17.5.1. Rifampicin resistance in any isolate from blood/CSF culture

17.5.1.1. Derivation

This is a binary outcome of 'Yes/No' for each baby. Rifampicin resistance can be found on

CRF "Form 5: Microbiology". Isolates from blood/CSF culture can be found under "Sample

Type" as any sample type except 'PICC tip'. Isolates from 'other' sample types will be referred

to the clinical team for confirmation of whether they should be included in analysis of this

outcome.

For rifampicin resistance to be tested, "organism cultured" must be anything except zero, and

the E-test must be selected as being performed. If the Rifampicin minimum inhibitory

concentration value is >0.5 mg/L then the sample is classed as being resistant to rifampicin.

If a baby has any sample which is rifampicin resistant, then this will be classed as "yes" for

that baby.

UK Standards for Microbiology Investigations⁷ details which organisms are classed as Gram-

negative and Gram-positive. The organisms cultured will be classified based on this.

17.5.1.2. Analysis

The analysis will use the method of Fisher's exact test to compare proportions of babies with

rifampicin resistance in the standard group compared to the impregnated group and relative

risks will be presented with 95% confidence intervals.

Frequency tables will be presented overall and split by treatment and gram negative/gram

positive samples.

Line listings of Rifampicin resistant isolates will be presented showing treatment and organism

cultured.

17.5.2. Rifampicin resistance in any isolate from PICC tips

17.5.2.1. Derivation

This is a binary outcome of 'Yes/No'. The definition of rifampicin resistance can be found in

section 17.5.1.1. Isolates from PICC tips can be found under "Sample Type" as type 3 (PICC

tip). If a baby has a PICC tip sample which is rifampicin resistant, then this will be classed as

"yes" for that baby.

UK Standards for Microbiology Investigations details which organisms are classed as Gram-

negative and Gram-positive. The organisms cultured will be classified based on this.

17.5.2.2. Analysis

The analysis will use the method of Fisher's exact test to compare proportions of babies with

rifampicin resistant PICC tips in the standard group compared to the impregnated group and

relative risks will be presented with 95% confidence intervals.

Frequency tables will be presented overall and split by treatment and gram negative/gram

positive samples.

Line listings of Rifampicin resistant isolates will be presented showing treatment and organism

cultured.

17.5.3. Type of organism isolated from BSI

17.5.3.1. Derivation

BSI is defined as in section 17.4.1.1. If there are multiple positive cultures within the primary

outcome time window, each positive culture will be assessed using the criteria in section

17.4.1.1 and the following (comparing positive cultures within the POTW as well as comparing

to positive cultures prior to POTW):

If the second positive culture is from the same isolate as the first and

there were less than 14 days between the two samples they should be

classified as the same episode of BSI.

o there were 14 days of more between the two samples they should be

classified as two independent episodes of BSI.

• If the second positive culture is from a different isolate to the first and

there were less than 24 hours between the two samples they should be

classified as the same episode of BSI.

o there were 24 hours or more between the two samples they should be

classified as two independent episodes of BSI.

The type of organism can be found on CRF "Form 5: Microbiology" under "Organism cultured".

Where a sample grows 3 or more different organisms, it is recorded as mixed growth rather

than as the individual organisms.

17.5.3.2. Analysis

This data will be presented descriptively with frequency tables split by treatment arm. No

formal statistical analysis will be undertaken.

17.5.4. Rate of BSI per 1000 PICC-days (including recurrent BSI)

17.5.4.1. Derivation

BSI is as defined in section 17.4.1.1. Where there are multiple positive cultures in the POTW,

independent episodes of BSI will be classified as in section 17.5.3.1. The total number of

independent episodes of BSI that occur when the line is in situ during the POTW should be

calculated for each baby and then summed to find the total number of BSI in each treatment

arm.

The number of days that the PICC is in situ for during the POTW can be calculated by

subtracting the date and time of the start of the POTW (Date and time of randomisation + 24

hours) from the date and time of PICC removal (or date and time of death if the baby died with

the line in situ). The date and time of PICC removal can be found on CRF "Form 6: Removal"

under section 1. The number of days should be summed to find the total number of days that

the PICC is in situ for during the POTW in each arm. For babies that did not have a line

inserted, this will be zero.

The rate of BSI per 1000 PICC-days is calculated as:

Total number of independent episodes of BSI that occur when line is in situ during POTW, across treatment arm $\times 1000$ Total number of days PICC is in situ for during the POTW (across treatment arm)

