17.3. Presentation of data for treatment adherence

Tables mentioned within this section will be presented overall and split by treatment.

Frequency tables (with percentages) will be presented for:

Reasons for PICC removal

• The number of babies whose PICC was removed less than 24 hours after

randomisation

The number of babies receiving the allocated PICC

The number of babies receiving a non-allocated PICC

The number of babies randomised but did not receive any PICC

The type of sample and whether an e-test was performed for positive cultures

• Length of time PICC is in situ for (from insertion to removal).

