17.5.6. Rate of catheter-related BSI per 1000 PICC days

17.5.6.1. Derivation

Catheter-related BSI is defined as "Yes" if the same organism is grown on the PICC-tip and blood/CSF sample. This information can found on CRF "Form 5: Microbiology" under "organism cultured". The total number of independent episodes of catheter-related BSI that occur when the line is in situ during the POTW should be calculated for each baby and then summed to find the total number of catheter-related BSI in each treatment arm. Where a baby has multiple positive cultures within the primary outcome time window they will be classified as single/multiple episodes of independent catheter-related BSI as in section 17.5.3.1.

The total number of days the PICC is in situ for during the POTW will be calculated using the derivation in section 17.5.4.1.

The rate of BSI per 1000 PICC-days is calculated as:

 $\frac{\textit{Total number of independent episodes of CR BSI that occur when line is in situ during POTW, across treatment arm}}{\textit{Total number of days PICC is in situ for during the POTW across treatment arm}}} \times 1000$

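### Section 17.5.4.1: PICC-days can come out negative after an early removal, or include line-free time after a late insertion; three secondary rates inherit the rule (wrong as written, minor)

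*SAP*

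**What the plan says.** Section 17.5.4.1 names its target plainly: "The number of days that the PICC is in situ for during the POTW can be calculated by" a subtraction. The start point comes from "subtracting the date and time of the start of the POTW (Date and time of randomisation + 24" and the end point follows: "hours) from the date and time of PICC removal (or date and time of death if the baby died with" the line in situ. Insertion time does not appear in the rule. One zero rule is given, opening "For babies that did not have a line" inserted. Nothing is said about a line that came out before the window opened.

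The numerator is confined to "independent episodes of BSI that occur when the line is in situ during the POTW should be" counted. Each rate is a ratio of arm totals times 1000, and section 17.5.4.2 asks for a rate ratio from Poisson regression without saying whether the fit uses babies or arm totals.

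Section 17.5.6.1 takes over the denominator: "The total number of days the PICC is in situ for during the POTW will be calculated using the derivation in section 17.5.4.1". Section 17.5.7.1 refers to the same derivation.

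Elsewhere the SAP plans to report both facts that the rule ignores. Section 17.3 tabulates "The number of babies whose PICC was removed less than 24 hours after" randomisation. Section 17.4.1.2 states "Differences between date and time of randomisation and date and time of insertion will be" summarised.

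**The concern.** The subtraction and the quantity it stands for are not the same. They agree when the line goes in within 24 hours of randomisation and comes out after 24 hours. They part in two situations:

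- **Removal, or death with the line in situ, before 24 hours.** True in-situ time within the window is zero, but the rule returns a negative number, which is then taken off the exposure of other babies in that arm.
- **Insertion after 24 hours.** The rule counts time before there was a line. Numerator events need a line in situ, so this time cannot carry an event.

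The first error makes a rate too high and the second makes it too low. If either situation were more common in one arm, the rate ratio would move. The first is foreseen by section 17.3. The second is possible on the text, but the SAP does not say how often, or whether, insertion comes that late.

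**Working it through.** The SAP states no PICC-day total, dwell time or expected rate, so there is no figure of its own to reproduce. The check compares two definitions, with times in hours from randomisation:

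- SAP rule: (removal or death in situ - 24) / 24 days; 0 if no line was inserted.
- Quantity named: max{0, (removal or death in situ) - max(24, insertion)} / 24 days.

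**Single babies**

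| Inserted | Removed | SAP rule (days) | Quantity named (days) |
|---|---|---|---|
| 2 h | 192 h | (192 - 24)/24 = 7.0 | 7.0 |
| 2 h | 12 h | (12 - 24)/24 = -0.50 | 0 |
| 1 h | 20 h | (20 - 24)/24 = -0.17 | 0 |
| 36 h | 192 h | 7.0 | (192 - 36)/24 = 6.5 |
| 72 h | 192 h | 7.0 | (192 - 72)/24 = 5.0 |

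The early-removal error cannot exceed 1 day per baby. The late-insertion error equals the delay beyond 24 hours.

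**Arm totals, main assumptions (none from the SAP).** 3% to 8% of lines are removed within 24 h of insertion, at a time uniform over those 24 h. The insertion delay D is exponential with mean μ of 3 to 16 h. Mean in-situ time is 9 to 10 days; 9.5 is used below.

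- Share inserted after 24 h: exp(-24/μ), which is 0.03% at μ = 3 and 22% at μ = 16.
- Mean line-free time credited per baby: μ·exp(-24/μ), which is 0.001 h at μ = 3 and 3.57 h = 0.149 days at μ = 16.
- Mean negative time per early removal: E[(24 - D)₊²]/48, which is 9.37 h = 0.391 days at μ = 3 and 4.29 h = 0.179 days at μ = 16.
- Mean days per baby under the SAP rule: 9.5 + μ/24 - 1.

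Most negative case (μ = 3, 8% early): the net error is -0.08 × 0.391 = -0.031 days. The SAP mean is 8.625 and the mean of the quantity named is 8.656, so the total is off by about -0.4%. About 7.0% of babies have negative days.

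Most positive case (μ = 16, 3% early): the net error is 0.149 - 0.03 × 0.179 = +0.143 days. The SAP mean is 9.167 and the mean of the quantity named is 9.023, so the total is off by +1.6%. About 1.4% of babies have negative days.

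Simulation under these assumptions agrees: the ratio of mean days is 0.996 to 1.016.

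**Arm totals, wider assumptions.** Take 429 babies per arm (858 / 2) and a mean of 4 to 10 PICC-days in the window.

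- 2% to 10% early removals at -0.5 day each: denominator 0.1% to 1.4% too small. For example, with 5% and a mean of 7 days: 0.05 × 429 × 0.5 = 10.7 days out of 0.95 × 429 × 7 = 2,853, or -0.4%.
- 5% to 10% of babies with 1 excess day: 0.5% to 2.5% too large.
- 10% with 3 excess days (insertion at 96 h): 3.0% to 7.5% too large.

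**Rate ratio, if the arms differ.** Early removals of 5% against 10%, at the limiting -1 day each, multiply it by 0.985 to 0.994. Late insertions of 15% against 5%, with 2 excess days each, multiply it by 0.95 to 0.98.

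**Poisson model.** A baby-level fit with a log-exposure offset needs positive exposure. A small test fit including exposures of -0.5 and 0 stopped with an error.

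**The case against.** The strongest reply is that the target is unmistakable and the edge cases are few. Negative time in situ is impossible, so a programmer would notice it and set it to zero. That may well happen, but the section deals expressly with death in situ and with babies who had no line, and gives no instruction for early removals or late insertions. Anyone correcting it would be departing from the written rule, and section 21 specifies independent programming for the primary analysis only.

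Several further points stand:

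- The late-insertion part is conditional. The SAP says only that the gap will be summarised. Babies with no line are censored 48 hours after randomisation (17.4.1.1), and reasons for not randomising after consent include the line no longer being needed (14.1). Both suggest randomisation close to insertion. The larger figures above need insertion at 72 to 96 hours and fit poorly with this.
- Sections 19.2.1 to 19.2.3 repeat all three rates over total in-situ time without the subtraction, so a material distortion should show there.
- A reader might infer that babies with negative or zero exposure would be lost from the Poisson model and bias it. The documents do not support this. The SAP does not specify a baby-level fit. If one is used, a baby with no in-situ time in the window can have no countable event, so leaving it out loses nothing. The corrected definition also gives zero for these babies.

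**Conclusion.** Wrong as written, minor. The rule in 17.5.4.1 does not equal the quantity it names, and 17.5.6 and 17.5.7 inherit it. The early-removal error rests on the text alone, in a situation the SAP itself tabulates. The late-insertion error occurs only if insertion follows randomisation by more than 24 hours, at a frequency the SAP does not give.

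The likely effect on pooled rates is small, about -0.4% to +1.6% of an arm's PICC-days, and this rests wholly on the assumed frequencies and dwell time. A reader might go further and infer that the three rates as a whole are unsound, or that the trial's conclusion is at risk. The documents do not support that: the rule is exact for lines inserted within 24 hours and removed later, these are three of sixteen secondary outcomes, and the primary outcome does not use this denominator. Nothing in the SAP shows that early removal or insertion delay differs between arms.

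**What to change.** In 17.5.4.1, define PICC-days for each baby as max{0, (removal or death in situ) - max(randomisation + 24 h, insertion)}, and keep zero for babies with no line. Count numerator events over exactly that interval. Add one sentence: babies with zero exposure contribute no days and no events, and are left out of any baby-level Poisson fit with a log-exposure offset. Carry the definition into 17.5.6.1 and 17.5.7.1, and say in the three analysis sections whether the Poisson model is fitted to babies or to arm totals.

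The cost is a line of derivation, a sentence on the model and a small program change. No new data are needed: section 19.1.2 already uses the date and time of insertion.
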